#### 5.8.4.3. Guidelines for cuSCC

Cutaneous squamous cell carcinoma have been observed in patients treated with dabrafenib and the combination of dabrafenib and trametinib (see dabrafenib and trametinib combination IB). These treatment-related cuSCC should be surgically removed according to institutional practice. Dose modifications or interruptions of the study treatment are not required for cuSCC. Occurrence of cuSCC must be reported as an SAE.

## 5.8.5. Guidelines for Other Adverse Event of Special Interest

## 5.8.5.1. Guidelines for Pyrexia

Episodes of pyrexia have been observed in patients receiving dabrafenib monotherapy or in combination with trametinib (see dabrafenib and dabrafenib and trametinib combination IBs). In a minority of cases the pyrexia was accompanied by symptoms such as severe chills, dehydration, hypotension, dizziness or weakness.

Pyrexia accompanied by hypotension, dehydration requiring IV fluids, or severe rigors/chills should be reported as an SAE per Section 7.4.2.2.

Patients should be instructed on the importance of immediately reporting febrile episodes. In the event of a fever, the patient should be instructed to take non-steroidal anti-pyretics as appropriate to control fever. In patients experiencing pyrexia associated with rigors, severe chills, dehydration, hypotension, etc., renal function should be monitored carefully (see Section 5.8.5.3).

Guidelines regarding management and dose reduction for pyrexia considered to be related to study treatment are provided in Table 12.

Table 12 Management and Dose Modification Guidelines for Pyrexia

Adverse Event	Adverse Event Management	Action and Dose Modification
Pyrexiaª	Clinical evaluation for infection and hypersensitivity c Laboratory work-up c Hydration as required d Administer anti-pyretic treatment if clinically indicated and continue prophylactic treatment e	Interrupt dabrafenib     Continue trametinib     Once pyrexia resolves to baseline, restart dabrafenib at the same dose level     If fever was associated with dehydration or hypotension, reduce dabrafenib by one dose level
	
 
2nd Event9
 
Clinical evaluation for infection and hypersensitivityc
 
Laboratory work-upc
 
Hydration as requiredd
 
Within 3 days of onset of pyrexia
 
Optimize anti-pyretic therapy
 
Consider oral corticosteroids (i.e., prednisone 10 mg) for at least 5 days or as clinically indicatedf
 
	
 
Interrupt dabrafenib
 
Continue trametinib
 
Once pyrexia resolves to baseline, restart dabrafenib at the same dose level
 
If fever was associated with dehydration or hypotension, reduce dabrafenib by one dose level
 

	
 
Subsequent Events:
 
Clinical evaluation for infection and hypersensitivityc
 
Laboratory work-upc
 
Hydration as requiredd
 
within 3 days of onset of pyrexia:
 
Optimize oral corticosteroid dose as clinically indicated for recalcitrant pyrexiaf
 
If corticosteroids have been tapered and pyrexia recurs, restart steroids
 
If corticosteroids cannot be tapered consult medical monitor
 
	
 
Interrupt dabrafenib
 
Continue trametinib
 
Once pyrexia resolves to baseline, restart dabrafenib reduced by one dose level
 
If dabrafenib must be reduced to <75 mg BID, permanently discontinue dabrafenib
 

- a. Pyrexia is defined as a body temperature equal to or above 38.5° Celsius or 101.3° Fahrenheit.
- b. For patients experiencing pyrexia complicated by rigors, severe chills, etc., a clinical evaluation and laboratory work-up is mandatory for each event; anti-pyretic treatment should be started immediately at the first occurrence and prophylactic anti-pyretic treatment is recommended
- c. Thorough clinical examination for signs and symptoms of infection or hypersensitivity is required; laboratory work-up should include full-blood-count, electrolytes, creatinine, blood urea nitrogen (BUN), C-reactive protein (CRP), liver-function tests, blood culture, and urine culture.
- d. Oral hydration should be encouraged in patients without evidence of dehydration. Intravenous hydration is recommended in patients experiencing pyrexia complicated by dehydration/hypotension.
- e. Anti-pyretic treatment may include acetaminophen, ibuprofen, or suitable anti-pyretic medication according to institutional standards. Prophylactic anti-pyretic treatment may be discontinued after three days in the absence of pyrexia
- f. In patient experiencing pyrexia complicated by rigors, severe chills, etc., which cannot be controlled with antipyretic medication, oral corticosteroids should be started at the 2nd event and doses should be gradually increased for subsequent events.
- g. Dabrafenib should be reduced by one dose level after three episodes of pyrexia complicated by rigors, severe chills, etc., which cannot be managed by best supportive care and increasing doses of oral steroids. Escalation of dabrafenib is allowed if no episode of pyrexia is observed in the 4 weeks subsequent to dose reduction.

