#### 5.8.1. Dose Levels of dabrafenib and trametinib

The dose levels for this study are provided in Table 4.

Table 4 Dose Level Reduction Guidelines

Dose Level	Dabrafenib Dose/Schedule	Trametinib Dose/Schedule	
Starting Dose	150 mg BID	2 mg once daily	
-1 (1st Dose reduction)	100 mg BID	1.5 mg once daily	
-2 (2 nd Dose reduction)	75 mg BID	1.0 mg once daily	

Abbreviation: BID = twice daily

If an AE resolves to grade 1 or baseline at the reduced dose level, and no additional toxicities are seen after 4 weeks of study treatment at the reduced dose, the dose may be increased to the previous dose level.

A dose reduction below 75 mg BID for dabrafenib and 1 mg once daily for trametinib is not allowed. If a dose reduction below 75 mg BID for dabrafenib is required, dabrafenib will be permanently discontinued, but the patient will be allowed to continue trametinib. If a dose reduction below 1.0 mg once daily for trametinib is required, then trametinib will be permanently discontinued, but these patients will be allowed to continue dabrafenib.

Note: Approval from the GSK Medical Monitor is required to restart study treatment after  $\geq$ 21 days of interruption.

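### In Table 12, the Subsequent Events cell and its footnote g give different conditions for the same one-level dabrafenib reduction, so a third or later uncomplicated or manageable fever has no single restart dose

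*Protocol*

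**What the plan says.** Section 5.8.5.1 limits Table 12 to fevers judged related to treatment: "Guidelines regarding management and dose reduction for pyrexia considered to be related to study treatment are provided in Table 12". Footnote a sets the event by temperature only: "Pyrexia is defined as a body temperature equal to or above 38.5° Celsius".

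The table has three tiers.

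- **First and second events.** Interrupt dabrafenib, then "restart dabrafenib at the same dose level". An exception is added: "If fever was associated with dehydration or hypotension, reduce dabrafenib by one dose level".
- **Subsequent events (third and later).** "Once pyrexia resolves to baseline, restart dabrafenib reduced by one dose level". The cell sets no severity condition. It adds that dabrafenib stops permanently if the next level would fall below 75 mg BID.
- **Footnote g**, whose marker follows that last instruction: "Dabrafenib should be reduced by one dose level after three episodes of pyrexia complicated by rigors, severe chills, etc", with the further requirement that these are episodes "which cannot be managed by best supportive care and increasing doses of oral steroids". It also permits re-escalation after four weeks without fever.

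Table 4 (Section 5.8.1) gives the dabrafenib levels as 150, 100 and 75 mg BID, and the text beneath it says: "If a dose reduction below 75 mg BID for dabrafenib is required, dabrafenib will be permanently discontinued". Nothing in Section 5.8 says whether the cell or the footnote prevails, and the Amendment 01 summary of changes does not touch Table 12.

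**The concern.** The cell and the footnote describe the same action, a one-level reduction, with different entry conditions. The cell needs only a third related fever at or above the temperature threshold. The footnote needs three episodes, all complicated and all beyond what supportive care and steroids can manage. A site that follows the cell and a site that follows the footnote can give the same patient different doses, and the difference can extend to stopping dabrafenib.

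The episodes on which the texts part are not an unusual kind of fever. Section 5.8.5.1 says that accompanying symptoms such as severe chills, dehydration or hypotension occurred in a minority of cases. Dabrafenib is taken from Day 1 in Arms A and C and from the start of the combination in Arm B, so exposure can be affected in all three arms.

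The SAP would not show the cause. It summarises dose reductions by number and reason (Section 12.1), but pools centres and plans no by-centre data summaries beyond recruitment (Section 8.2). It also lists and summarises all protocol deviations (Section 10.2), and a site that follows either text could be recorded as deviating from the other.

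**Working it through.** There is no planned figure to reproduce. The check sets the two texts side by side and then traces the dose.

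**Step 1. Does a reduction apply after the third related fever?** Assume no dehydration or hypotension at events 1 and 2.

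| Patient's fevers | Subsequent Events cell | Footnote g trigger |
|---|---|---|
| Three uncomplicated | Reduce | Not met |
| Three with rigors, settled by supportive care or steroids | Reduce | Not met |
| Two uncomplicated, third complicated and unmanageable | Reduce | Not met (one qualifying episode, not three) |
| Three complicated and unmanageable | Reduce | Met |

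The texts agree only in the last line.

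**Step 2. Dose trace.** Inputs: starting dose 150 mg BID and the 100 and 75 mg BID levels (Table 4), with permanent discontinuation below 75 mg BID (Section 5.8.1). The patient has repeated related fevers that are uncomplicated or manageable, no dehydration or hypotension at events 1 and 2, and no re-escalation.

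| Related fever | Dose at restart under the cell | Share of starting daily dose | Footnote g trigger |
|---|---|---|---|
| 1 and 2 | 150 mg BID | 300/300 = 100% | Not met |
| 3 | 100 mg BID | 200/300 = 67% | Not met |
| 4 | 75 mg BID | 150/300 = 50% | Not met |
| 5 | Dabrafenib permanently discontinued | 0% | Not met |

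The readings part at the third fever.

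**Step 3. Can the footnote be read as limiting the cell?** If so, the reduction no longer applies to the patient in Step 2. But the instruction to restart at an unchanged dose sits only in the first- and second-event rows. The Subsequent Events row offers no alternative to the reduction. The conflict becomes a gap: no restart dose is stated for that patient. Staying at 150 mg BID would be an inference.

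**Step 4. Later episodes.** Where three fevers were complicated and unmanageable, both texts give one reduction. At the fourth, the cell reduces again. The footnote does not say whether one more episode is enough or three more are needed.

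**The case against.** The strongest reply is that this is one qualified instruction. The footnote marker sits on the reduction itself, and the protocol elsewhere puts conditions on dose actions in footnotes (Tables 8, 10 and 14). Footnote g does not say that a reduction is allowed only under its conditions. This stands as a possible reading, but Step 3 shows that it leaves a gap, so the text still needs correction.

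Several stronger readings are tempting, and the documents do not support them.

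- **A three-way contradiction.** A reader might infer that the dehydration and hypotension lines are a third incompatible rule. They appear only for events 1 and 2, so a site can follow them together with the later row.
- **A misplaced footnote.** A marker resembling g also appears beside the second-event heading in the extracted text. Superscripts in this table are not reliably preserved, so nothing should rest on it.
- **The dose rule used most often.** Pyrexia occurred in 52% of Part B patients, and as a treatment-related event in 58% at 150 mg BID with 2 mg once daily (Section 1.1.3). These are rates of any pyrexia. No rate of three or more episodes is given.
- **A biased primary endpoint.** The p-ERK changes run from baseline to Week 2 and from Week 8 to Week 10. In a patient newly on the combination, a third related fever would have to occur, resolve and be followed by restart within about two weeks. Nothing in the documents says how often that would happen. The study is descriptive, without treatment comparisons.

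**Conclusion.** The point holds as an inconsistency within one table. For third or later treatment-related fevers that are uncomplicated or manageable, the Subsequent Events cell and footnote g either conflict or leave the restart dose unstated. For three complicated, unmanageable fevers they agree on the first reduction but not clearly on any later one.

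For a single patient the difference can be large: from the starting dose to permanent discontinuation of dabrafenib by the fifth fever. That path assumes related fevers only, no earlier reduction for dehydration or hypotension, and no re-escalation. The protocol allows re-escalation after four weeks, which would slow or interrupt the descent.

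The number of patients affected cannot be estimated from the documents. That sites will differ is a foreseeable result of two texts, not something the documents report. The matter is worth correcting because it bears on patient safety and on consistent dabrafenib exposure. This review takes no position on which rule is clinically right.

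**What to change.** The sponsor should reconcile the Subsequent Events cell and footnote g of Table 12 so that one text states:

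- which episodes count towards a reduction (any related fever, or only those meeting stated conditions);
- at which episode a reduction applies, and the restart dose when it does not;
- whether each later episode triggers a further reduction;
- how the rule fits with the dehydration and hypotension lines for events 1 and 2.

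The sponsor's clinical team decides which rule stands. The cost is a wording change to one table in a protocol amendment, with no added procedures or patients.

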#### 5.8.5.2. Guidelines for Diarrhoea

Episodes of diarrhoea have occurred in patients receiving dabrafenib, trametinib, or both therapies in combination. Other, frequent causes for diarrhoea including concomitant medications (e.g., stool softeners, laxatives, antacids, etc.), infections by *C. difficile* or other pathogens, partial bowel obstruction, etc., should be clinically excluded.

Guidelines regarding management and dose reduction for diarrhoea considered to be related to study treatment by the investigator are provided in Table 13.

Table 13 Management and Dose Modification Guidelines for Diarrhoea

CTCAE Grade	Adverse Event Management	Action and Dose Modification
Uncomplicated Diarrhoea a	Diet: stop all lactose containing products; eat small meals, BRAT-diet (banana, rice, apples, toast) recommended	Continue study treatment  If diarrhoea is grade 2 for > 48h, interrupt study treatment until diarrhoea
Grade 1 or 2	Hydration: 8-10 large glasses of clear liquids per day (e.g., Gatorade or broth)  Loperamidec: initially 4 mg, followed by 2 mg every four hours or after every unformed stool; maximum 16 mg/day. Continue until diarrhoea free for 12 hours  Diarrhoea > 24h: loperamide 2 mg every two hours; maximum 16 mg/day. Consider adding oral antibiotics  Diarrhoea > 48h: loperamide 2 mg every two hours; maximum 16 mg/day. Add budesonide or other second-line therapies (otreotide, or tincture of opium) and oral antibiotics	resolves to grade ≤1  Restart study treatment at the same dose level
Uncomplicated Diarrhoea a Grade 3 or 4 Any Complicated Diarrhoea b	Clinical evaluation mandatory  Loperamidec: initially 4 mg, followed by 2 mg every four hours or after every unformed stool; maximum 16 mg/day. Continue until diarrhoea free for 12 hours  Oral antibiotics and second-line therapies if clinically indicated  Hydration: intravenous fluids if clinically indicated  Antibiotics (oral or intravenous) if clinically indicated  Intervention should be continued until the patient is diarrhoea free for ≥ 24 hours  Intervention may require hospitalization for patients at risk of life-threatening complications	Interrupt study treatment until diarrhoea resolves to grade ≤1  Restart with study treatment reduced by one dose level d If 3 dose reductions of study treatment are clinically indicated, permanently discontinue study treatment

Abbreviation: CTCAE = Common Terminology Criteria for Adverse Events

- a. **Uncomplicated diarrhoea** defined by the absence of symptoms such as, cramping, nausea/vomiting ≥grade 2, decreased performance status, pyrexia, sepsis, neutropenia grade ≥3, frank bleeding, and/or dehydration requiring intravenous fluid substitution
- b. **Complicated diarrhoea** defined by the presence of symptoms such as, cramping, nausea/vomiting ≥grade 2, decreased performance status, pyrexia, sepsis, neutropenia grade ≥3, frank bleeding, and/or dehydration requiring intravenous fluid substitution
- c. Loperamide should be made available prior to start of study treatment so loperamide administration can begin at the first signs of diarrhoea
- d. Escalation of study treatment to previous dose level is allowed after consultation with the medical monitor and in the absence of another episode of complicated or severe diarrhoea in the 4 weeks subsequent to dose reduction.

### 5.8.5.3. Guidelines for Renal Insufficiency

Cases of renal insufficiency have occurred in patients receiving dabrafenib and the combination of dabrafenib and trametinib. Prior to start of study treatment, concomitant medications should be reviewed for the potential risk of inducing nephrotoxicity and concomitant medications should be modified if clinically possible.

Guidelines regarding management and dose reduction for renal insufficiency considered to be related to study treatment by the investigator are provided in Table 14.

Table 14 Management and Dose Modification Guidelines for Renal Insufficiency

Serum Creatinine Level	Adverse Event Management	Action and Dose Modification
Serum creatinine increase >0.2 mg/dL (18 umol/L) but ≤0.5 mg/dL (44 umol/L) above baseline	Recheck serum creatinine within  1 week  Serum creatinine increase > 1 week: contact GSK Medical Monitor  If pyrexia is present, treat pyrexia as per guidelines a	Continue study treatment at the same dose level
Serum creatinine increase >0.5 mg/dL (44 umol/L) above baseline or serum creatinine >2 mg/dL (> 177 umol/L)	Monitor serum creatinine ≥ 2- times per week  Hospitalization may be necessary if serum creatinine cannot be monitored frequently  If pyrexia is present, treat pyrexia per guidelines a Consult nephrologist if clinically indicated  Perform renal biopsy if clinically indicated, for example:  Renal insufficiency persists despite volume repletion  Patient has new rash or signs of hypersensitivity (such as elevated eosinophil count)	Interrupt study treatment until serum creatinine recovers to baseline  Restart with study treatment b

Abbreviations: GSK = GlaxoSmithKline; NSAIDS = non-steroidal anti-inflammatory drugs

- NSAIDs can induce renal insufficiency, especially in patients with dehydration; encourage oral fluids or consider intravenous fluids as clinically indicated. See guidelines for pyrexia 5.8.5.1.
- b. Investigator may restart at either the same or a reduced dose level. Escalation of study treatment to previous dose level is allowed if another episode of renal insufficiency does not occur after 4 weeks of dose reduction. Consultation with GSK Medical Monitor is required before restarting study treatment if there is evidence of thrombotic microangiography.

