Total bilirubin	≤ 1.5 x ULN
AST and ALT	≤ 2.5 x ULN
Renal	,
Calculated creatinine clearance b	≥50 mL/min
Cardiac	
Left Ventricular Ejection fraction (LVEF)c	≥ LLN by ECHO

- Abbreviations: ALT = alanine transaminase; ANC = absolute neutrophil count; AST = aspartate aminotransferase;
   INR = international normalized ratio; LLN = lower limit of normal; PT = prothrombin time; PTT = partial thromboplastin time; ULN = upper limit of normal.
- b. Patients receiving anticoagulation treatment may be allowed to participate with INR established within the therapeutic range prior to randomisation. PT and PTT >1.5 ULN are permitted in these patients.
- Calculate creatinine clearance using standard Cockcroft-Gault formula (Appendix 2). Creatinine clearance must be ≥50 mL/min to be eligible.
- d. ECHO scans must be used throughout the study
- 12. In France, a patient will be eligible for inclusion in this study only if either affiliated to, or a beneficiary of, a social security category.

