# **Appendix 2 Cockcroft-Gault Formula**

To determine eligibility for the study, investigators should calculate a patient's creatinine clearance by the Cockcroft-Gault formula as follows [Cockcroft, 1976]:

$$72 \times (\text{serum creatinine [mg/dL]})$$

CrCL for females 
$$\underbrace{0.85 \times (140 \text{ - age [years]}) \times (\text{weight})}_{\text{[kg]}}$$

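### Protocol Table 14: a treatment-related creatinine rise of >0.2 to ≤0.5 mg/dL that ends above 2 mg/dL meets both the continue row and the interrupt row, and no precedence is stated

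*Protocol*

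**What the plan says.** Section 5.8.5.3 limits the table's scope: guidelines for "renal insufficiency considered to be related to study treatment by the investigator are provided in Table 14". The table has two rows.

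- **Row 1** is triggered by "Serum creatinine increase >0.2 mg/dL (18 umol/L) but ≤0.5 mg/dL (44 umol/L) above baseline". The dosing action is "Continue study treatment at the same dose level". Creatinine is rechecked within 1 week, with a further step if the increase lasts: "Serum creatinine increase > 1 week: contact GSK Medical Monitor".
- **Row 2** is triggered by "Serum creatinine increase >0.5 mg/dL (44 umol/L) above baseline or serum creatinine >2 mg/dL (> 177 umol/L"). The dosing action is "Interrupt study treatment until serum creatinine recovers to baseline". Creatinine is checked at least twice per week.

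The table's footnotes deal with NSAIDs and hydration, the dose at restart, and later re-escalation. Sections 5.8, 5.8.1 and 5.8.2 contain no rule for choosing between rows. Table 5 covers only related events without their own guidelines, so it does not apply. The SAP does not address the point.

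Renal eligibility is set by clearance, not by creatinine (Section 4.1.2, Table 2 notes): "Creatinine clearance must be ≥50 mL/min to be eligible". Appendix 2 tells investigators to calculate "creatinine clearance by the Cockcroft-Gault formula as follows".

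**The concern.** Row 1 has a lower and an upper limit on the rise but no limit on the value reached. Row 2 has a limit on the rise and, as an alternative, a limit on the value. A patient whose creatinine climbs by a moderate amount from a raised baseline can therefore satisfy both conditions at once, and the two dosing instructions are opposite.

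A site that applied row 1 to such a patient would continue full dosing at a creatinine above the protocol's own interruption threshold. It would recheck within a week and call the Medical Monitor only if the increase lasted longer than a week. A site that applied row 2 would stop the drug and check at least twice weekly. Both could cite the table.

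**Working it through.** **Inputs.** Row conditions and actions: Table 14. Eligibility: clearance of at least 50 mL/min, Section 4.1.2. Clearance formula: Appendix 2. The plan states no figure here that could be reproduced.

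**1. Where the rows overlap.** Let b be baseline and v the on-treatment value, in mg/dL.

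- Row 1: 0.2 < v − b ≤ 0.5
- Row 2: v − b > 0.5, or v > 2

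Both hold when max(2, b + 0.2) < v ≤ b + 0.5. This range is non-empty only if b + 0.5 > 2, that is, b > 1.5.

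| Baseline | Values meeting both rows |
|---|---|
| 1.5 | none (1.5 + 0.5 = 2.0, which is not above 2) |
| 1.6 | above 2.0, up to 2.1 |
| 1.7 | above 2.0, up to 2.2 |
| 1.8 | above 2.0, up to 2.3 |
| 1.9 | above 2.1, up to 2.4 |
| 2.0 | above 2.2, up to 2.5 |

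The band is never wider than 0.3 mg/dL. Example: 1.7 to 2.1 is a rise of 0.4 and meets both rows.

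**2. Whether such a baseline can be enrolled.** Clearance = (140 − age) × weight × f / (72 × creatinine), with f = 1 for men and 0.85 for women. Ages and weights below are illustrative assumptions.

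- Man, 50 y, 80 kg, creatinine 1.7: 90 × 80 / (72 × 1.7) = 7200 / 122.4 = 58.8 mL/min. Eligible.
- Woman, 50 y, 80 kg, creatinine 1.6: 0.85 × 7200 / (72 × 1.6) = 6120 / 115.2 = 53.1 mL/min. Eligible.
- Woman, 50 y, 65 kg: highest eligible creatinine is 90 × 65 × 0.85 / 3600 = 1.38. The overlap is out of reach.

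In general a baseline above t is eligible only if weight > 3600 × t / (f × (140 − age)). For t = 1.5 the limits for men/women are 60.0/70.6 kg at 50 y and 77.1/90.8 kg at 70 y. The overlap is reachable, but only in heavier or younger patients with raised creatinine.

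**3. Which row makes sense.** Take 1.90 to 2.05. The rise is 0.15, so row 1 does not apply; the value exceeds 2, so row 2 does, and dosing is interrupted. If row 1 governed in the overlap, a patient going from 1.8 to 2.3 (rise 0.5) would continue. The larger rise to the higher value would get the weaker action. Only giving row 2 precedence avoids that.

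**4. Whether a cap cures it.** With v ≤ 2 added, row 1 requires 0.2 < v − b ≤ 0.5 and v ≤ 2. For rises above 0.2, that is exactly the complement of row 2. No case meets both rows and no rise above 0.2 is left without a row.

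**5. Baseline already above 2.** This is also possible: the weight limit for t = 2.0 in a 40-year-old man is 3600 × 2 / 100 = 72.0 kg. Such a patient meets the absolute limb of row 2 with no rise at all, and still meets it after recovering to baseline. Neither the cap nor a precedence rule settles this.

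**The case against.** The best answer is that the table has one workable reading. The word joining the two limbs of row 2 makes a value above 2 mg/dL sufficient on its own, the rows ascend in severity, and most investigators would probably interrupt. Table 7 on hypertension is built the same way: a persistent, asymptomatic pressure of 165/95 mmHg meets Scenario A through its diastolic limb and Scenario B through its systolic limb, again with no sentence on precedence. On this view the section relies on readers taking the higher row, and the point is one of drafting. Much of that stands, and it is why the point is minor. But precedence has to be inferred, and a site that continued dosing could point to row 1 word for word. The liver rule in Section 5.9.1.2 shows the protocol can close the gap: its continue rule is capped (ALT below 5 and bilirubin below 2 times ULN), and it sends any patient who meets a stopping criterion to the stopping rule. Nor can the Study Procedures Manual supply the missing words, because Section 3 confines it to material without impact on patient safety.

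It is also fair that the consequence is hypothetical and narrow. It needs a raised baseline, a treatment-related rise into a band at most 0.3 mg/dL wide, and a reader who overlooks the adjacent row. Exclusion criterion 7 may also remove patients with serious or unstable conditions. Even under row 1 there is a recheck within a week.

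A reader might infer that the absolute limb of row 2 has no purpose unless it overrides row 1, and that this proves the intent to interrupt. It does not: the limb also catches rises of 0.2 mg/dL or less that end above 2, and baselines already above 2. The case for interruption rests on coherence (step 3), not on proof of intent.

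**Conclusion.** The conflict is real on the face of Table 14. For a baseline above 1.5 mg/dL, a related rise of more than 0.2 and up to 0.5 mg/dL that ends above 2 mg/dL carries two opposite dosing instructions, with no stated precedence. Interruption is the only coherent reading, but the intent is inferred, and row 1 as written permits dosing to continue.

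The weight is small. The eligibility examples rest on assumed ages and weights; they show that the case can occur, not how often. A reader might infer that some number of the 54 patients would be affected. The documents give no baseline creatinine distribution and do not support any count; it may be zero. Nor does anything here bear on the pERK endpoint, the sample size or the planned analyses. This is a minor wording error in a safety rule, worth correcting when the protocol is next amended.

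**What to change.** Add *and serum creatinine ≤2 mg/dL (≤177 umol/L)* to the row 1 condition of Table 14. Alternatively, add a footnote that the more severe row governs when both are met. Either removes the conflict.

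State separately which limb applies to an eligible patient whose baseline is already above 2 mg/dL, for example the rise limb only. If that option is combined with the cap, exempt these patients from the cap as well. Otherwise a rise from 2.1 to 2.4 mg/dL would fall in neither row.

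The cost is a phrase or footnote, plus one sentence for the high-baseline case, at the next amendment. Assessments, sample size and analysis do not change.
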